7.11 Visit Windows

Study visits will be windowed as given in Section 4.1. Data values will be presented for all scheduled study visits according to the nominal day obtained from the CRF (e.g., data value obtained on Day 9 within visit window Day 8+/-1).

If an unscheduled visit falls into a visit window with an existing scheduled assessment, the scheduled assessment will be used for summary presentation. Otherwise, if no scheduled assessment exists for a visit window but unscheduled visits are available within the same visit window, the unscheduled

Statistical Analysis Plan

FK Study Identifier: SMOF-018-CP3

assessment obtained closest to the midpoint of the visit window will be used for summary presentation. If there is no scheduled visit assessment for a visit window but unscheduled assessments outside of this visit window, then the unscheduled assessment obtained closest to the midpoint of the visit window but not beyond +/-3 days from the midpoint will be used for summary presentation. In case of ties, the latest assessment will be used.

All scheduled and unscheduled values will be included in the data listings.

Version (of CSP): 3.0

CONFIDENTIAL

page 31 of 56

date: 5 OCT 2020

████████████████████
Annex No.: 00
Document No.: 1 ██████████

Date:
Page:

████████████████████
31 of 56

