	Screening	Day 1 Baseline	Day 8	Day 15	Day 22	Day 29 / End of Treatment ^a	Day 36	Day 43	Day 50	Day 57	Day 64	Day 71	Day 78	Day 85 / End of Treatment ^a	
Time Window (d)	Day 1 -3d	0	±1	±1	±1	+1	±2	±2	±2	±2	±2	±2	±2	+1	±1
Parent Informed Consent	X														
In- / Exclusion Criteria	X	X													
Randomization		X													
Demographics incl. race and ethnicity	X														
Medical History	X														
Prior Medication	X														
Physical Examination	X	X	X	X	X	X	X	X	X	X	X	X	X	X	X
Vital Signs	X	X	X	X	X	X	X	X	X	X	X	X	X	X	X
Body Length		X	X	X	X	X	X	X	X	X	X	X	X	X	X
Head Circumference		X	X	X	X	X	X	X	X	X	X	X	X	X	X
Time to Full Enteral or Oral Feeds						X									X
Length of Stay															X
Blood Sampling for Conjugated Bilirubin ^b	X		X	X	X	X		X		X		X		X	(X) ^c
Blood Sampling for Biochemistry, Hematology and Coagulation ^d	X		X	X	X	X		X		X		X		X	
Blood Sample for special analyses ^e		X				X			X					X	

^a: End of treatment visit to be performed on the following day after receiving the last dose of study medication

^b: If conjugated bilirubin exceeds 1.5 mg /dL it has to be assessed weekly, also after d29

^c: If conjugated bilirubin is > 1.5 mg/dL at the end of treatment visit a blood sample for the assessment of conjugated bilirubin has to be drawn at the Follow-up Visit

^d: Additional blood samples for assessment of TGs and blood glucose need to be drawn during ramp up of lipid dose. Should TGs exceed 250 mg/dL at any time, lipids will be withheld until analysis of TGs in another blood sample the following morning.

^e: Special analyses: Fatty acids, sterols, α-Tocopherol

Clinical Study Protocol SMOF-018-CP3
Smoflipid 20% lipid injectable emulsion

3 Contents

RESPONSIBILITIES (SIGNATURE PAGE)	3
1 STUDY OUTLINE.....	6
2 STUDY SCHEDULE	16
3 CONTENTS.....	17
3.1 LIST OF TABLES	20
3.2 LIST OF FIGURES	20
4 TABLE OF ABBREVIATIONS	21
5 INTRODUCTION.....	23
5.1 BACKGROUND.....	23
5.2 RATIONALE AND PURPOSE OF THE STUDY	24
5.3 BENEFIT/RISK ASSESSMENT.....	24
6 OBJECTIVES	25
6.1 STUDY HYPOTHESIS.....	25
6.2 STUDY VARIABLES	25
6.2.1 Primary Variable	25
6.2.2 Secondary Variable(s)	26
7 STUDY DESIGN.....	27
7.1 DESCRIPTION OF THE STUDY DESIGN	27
7.2 RATIONALE OF STUDY DESIGN, INCLUDING CHOICE OF CONTROL GROUP	29
7.3 RANDOMIZATION, ALLOCATION OF PATIENTS	30
7.4 BLINDING AND DECODING	31
8 DATA MANAGEMENT AND STATISTICS	32
8.1 DATA MANAGEMENT.....	32
8.2 STATISTICS.....	33
8.2.1 Study Outcome Measures	33

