5.3 Benefit/Risk Assessment

Study patients will receive the study drugs as part of their nutritional support for at least 28 days during their hospitalization. It is standard clinical practice to incorporate lipid emulsions into the PN protocol in patients in whom enteral or oral nutrition is not sufficient or not feasible. The alternative treatment, (i.e., supply of calories by large amounts of dextrose, or dextrose exclusively) is associated with metabolic complications and liver damage and, therefore, is not appropriate ([Koletzko, et al. 2005](#)).

In neonates, and specifically in preterm neonates, an inadequate supply of EFAs and/or their derived long-chain polyunsaturated fatty acids during the critical periods of rapid brain growth and retinal development may lead to long-term impairment of neurodevelopment and visual

Clinical Study Protocol SMOF-018-CP3 Smoflipid 20% lipid injectable emulsion

function ([Clandinin, et al. 1980, Koletzko 1992, Lapillonne 2014](#)). Essential fatty acids and polyunsaturated fatty acids cannot be synthesized from other metabolites and need to be provided to the neonates as part of their nutritional regimen. Therefore, the administration of IVLEs has to be initiated within days of birth in neonates who cannot be fed enterally ([Driscoll, et al. 2008](#)).

Both study drugs are approved in more than 60 countries. In addition, the comparator drug Intralipid is approved for use in the US. Like any other injectable lipid preparation, uncommon side effects of Smoflipid may include hypertriglyceridemia, nausea, chills, thrombocytopenia, cholestasis, and hepatic impairment after long-term treatment. However, since its introduction in 2006, no particular safety issue regarding the use of Smoflipid has been identified. In contrast, in the phase 1 study performed by Fresenius Kabi, the increase in serum triglyceride (TG) concentrations during infusion of Smoflipid was less pronounced, and elimination of TGs after the end of infusion was faster than during infusion of the standard soybean emulsion Lipovenös® 20%. This difference was probably due to the MCT portion in Smoflipid. It is expected that the fatty acid profile of Smoflipid will have a beneficial effect on the hepatic health patients compared to Intralipid ([Driscoll, et al. 2008, Rangel, et al. 2012, Vanek, et al. 2012](#)). The purpose of the present study is to confirm this beneficial effect.

6 Objectives

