10.3 Exclusion Criteria

1. Conjugated bilirubin > 0.6 mg/dL
2. Any known pre-, intra- or posthepatic complication that will increase conjugated bilirubin levels > 0.6 mg/dL during study participation
3. Suspected liver disease or damage based on either AST, ALT, or GGT exceeding $2.5 \times$ upper limit of normal range
4. Active bloodstream infection demonstrated by positive blood culture at screening
5. Cystic fibrosis
6. Meconium ileus
7. Serum TGs > 250 mg/dL
8. Cyanotic congenital heart defect
9. Severe renal failure as evidenced by creatinine > 2.0 mg/dL
10. History of shock requiring vasopressors
11. Anasarca
12. Extracorporeal Membrane Oxygenation (ECMO)
13. Known inborn errors of metabolism
14. Known congenital viral infection
15. Unlikely to survive longer than 28 days
16. Known hypersensitivity to fish-, egg-, soya- or peanut protein, or to any of the active substances or excipients

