The target lipid dose is 3 g/kg/day. In patients that are already receiving PN before starting study treatment, the lipid dose will either stay at 3.0 g/kg/day or increased in 1g/kg/day steps to a maximum of 3.0 g/kg/day. In patients that have not yet started PN prior to study participation, lipid dose will be increased stepwise using the following regimen:

Study Day	Patients < 1500 g	Patients \geq 1500 g
Day 1	1.0 g/kg/day	2.0 g/kg/day
Day 2	2.0 g/kg/day	3.0 g/kg/day
Day 3+	3.0 g/kg/day	3.0 g/kg/day

The investigational or control drug will be infused over 20 - 24 hours, as per hospital policy, at a weight based infusion rate. The respective hospital policy will be filed in the investigator site file. If the blood draw is from the PN/lipid infusion line, then lipid (study drug) should be held for 4 hours prior to the time of blood sampling.

Blood samples for TGs and blood glucose monitoring during dose ramp-up will be taken as follows:

Neonates < 1500 g: At 1 g/kg/day, 2 g/kg/day and first dose of 3 g/kg/day
Neonates \geq 1500 g: At first dose of 3 g/kg/day

Clinical Study Protocol SMOF-018-CP3 **Smoflipid 20% lipid injectable emulsion**

Once the target dose has been reached, TGs must be checked weekly.

Should TGs exceed 250 mg/dL at any time, lipids will be withheld until analysis of another blood sample the following morning. If TGs are then \leq 250 mg/dL, lipids will be restarted. If not, this procedure will be repeated the next morning.

Conjugated bilirubin values must be assessed weekly. If the conjugated bilirubin level exceeds 1.5 mg/dL, the lipid dose must be decreased to 1 g/kg/day. Dextrose will be increased accordingly to maintain adequate energy provision. Once the lipid dose is minimized to 1 g/kg/day, it will not be increased again.

If conjugated bilirubin exceeds 2 mg/dL the patient's dose will remain at 1 g/kg/day until analysis of the next weekly blood sample. If conjugated bilirubin has increased further by at least 1 mg/dL, the patient must be withdrawn from the study and the Investigator will use institutional standard of care for the provision of PN. If not, the patient will remain in the study and will continue to receive study medication. Weekly conjugated bilirubin analyses should be performed until the patient's conjugated bilirubin level is again \leq 1.5 mg/dL.

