Annex No.:
Document No.:

00
1

Date:
Page:

18 of 56

Statistical Analysis Plan

FK Study Identifier: SMOF-018-CP3

^b: If conjugated bilirubin exceeds 1.5 mg /dL it has to be assessed weekly, also after d29

^c: If conjugated bilirubin is > 1.5 mg/dL at the end of treatment visit a blood sample for the assessment of conjugated bilirubin has to be drawn at the Follow-up Visit

^d: Additional blood samples for assessment of triglycerides (TGs) and blood glucose need to be drawn during ramp up of lipid dose. Should TGs exceed 250 mg/dL at any time, lipids will be withheld until analysis of TGs in another blood sample the following morning.

^e: Special analyses: Fatty acids, sterols, α -Tocopherol

Version (of CSP): 3.0

CONFIDENTIAL

page 19 of 56

date: 5 OCT 2020

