8.12.5 Clinical Laboratory

Laboratory assessments and change from baseline will be summarized with descriptive statistics by test panel, individual laboratory test, underlying disease and group treatment group, and time point. Additionally, abnormal results including normal, abnormal clinically significant (abnormal CS), abnormal not clinically significant (abnormal NCS) captured by the eCRF will be summarized with

Statistical Analysis Plan

FK Study Identifier: SMOF-018-CP3

frequencies and percentages by clinical significance, panel, test, underlying disease group and treatment group, and time point. The denominators for percentages will be the number of patients in the analysis set for the treatment group summarized. Missing values will be presented in the summary tables. Counts and percentages of patients with shifts for the period from baseline to the end of the initial treatment phase will be summarized by analyte, underlying disease group and treatment group:

- Normal -> abnormal CS: from normal at Baseline (Day 0 or Day 1) to abnormal CS at the end of the initial treatment phase
- Normal -> abnormal NCS: from normal at Baseline to abnormal NCS at the end of the initial treatment phase
- Abnormal NCS -> abnormal CS: from abnormal NCS at Baseline to abnormal CS at the end of the initial treatment phase
- In addition, counts and percentages of patients with shifts for the period from baseline to the end of the extended treatment phase will be summarized by analyte and treatment group as described above. In this table, the denominator will be number of patients still in the study at the end of the initial treatment phase.

A data listing will display all laboratory test results and findings. A listing of lab data (including all visits) for patients who had at least one abnormal result will be provided.

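### No planned table gives the per-infant incidence of triglycerides above 250 mg/dL, the protocol's lipid-hold trigger, and the by-visit summaries leave out the ramp-up samples

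*SAP*

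**What the plan says.** Serum TG is a listed safety variable (SAP 5.2.2). Protocol 5.3 says that "uncommon side effects of Smoflipid may include hypertriglyceridemia", as with other injectable lipids. Protocol 10.3 excludes infants with "Serum TGs > 250 mg/dL", so a later exceedance is new.

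During treatment the protocol adds TG samples to the weekly ones. Footnote d of its study schedule states: "Additional blood samples for assessment of TGs and blood glucose need to be drawn during ramp up of lipid dose". Protocol 11.3 gives the sampling points: "Neonates < 1500 g: At 1 g/kg/day, 2 g/kg/day and first dose of 3 g/kg/day", and only the first 3 g/kg/day dose for heavier infants. The same section sets the trigger: "Should TGs exceed 250 mg/dL at any time, lipids will be withheld until analysis of another blood sample the following morning".

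On the analysis side, SAP 8.12.5 says: "Laboratory assessments and change from baseline will be summarized with descriptive statistics by test panel", and continues by individual test, disease group, treatment and time point. It adds counts of normal, abnormal clinically significant and abnormal not clinically significant results by time point, and shifts from baseline to the end of each phase. SAP 7.11 decides which value stands for a visit. A scheduled value takes precedence. Without one, an unscheduled value inside the window is used. Failing that, the value used is the one "closest to the midpoint of the visit window but not beyond +/-3 days from the midpoint will be used for summary presentation". All values are to go into listings.

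**The concern.** The protocol treats 250 mg/dL as an action threshold and requires extra samples at the dose steps to detect it. The obvious safety question is how many infants in each arm crossed it. Nothing in SAP 8.12.5 or in the SAP section 9 table index answers that. A visit mean or median does not give the number of infants above a threshold, and the clinical-significance categories follow investigator judgement rather than the 250 mg/dL cut.

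The SAP treats the protocol's bilirubin rules differently. Lipid minimization, withdrawal for bilirubin, area above 1.5 mg/dL and time to more than 2 mg/dL each have a table. The TG rule has no counterpart. If this stays, the report can describe average TG at weekly visits but cannot state TG intolerance by arm, and the samples drawn while the dose is being raised do not contribute to the TG summaries.

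**Working it through.** The documents give no rate of TG above 250 mg/dL, so there is no planned figure to reproduce. The check has three parts.

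**1. Which samples reach a by-visit summary**

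- Scheduled biochemistry after the first dose (study schedule): Days 8, 15, 22 and 29 in the initial phase.
- Ramp-up days for infants starting parenteral nutrition in the study (Protocol 11.3 dose table): Days 1, 2 and 3 below 1500 g; Day 2 at or above 1500 g. Each is one day later if the sample is drawn the next morning, so Day 4 at the latest when the schedule is kept.
- Earliest day that can stand for Day 8 under SAP 7.11: 8 − 3 = Day 5, and only if Day 8 has no scheduled value.

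Since 4 < 5, no on-schedule ramp-up sample can enter Day 8. The only visit within 3 days is Day 1, which has no scheduled biochemistry. SAP 7.9 defines baseline as the last value before first administration, so a post-dose value does not belong there.

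Share of required samples outside the Day 8 to Day 29 summaries, in this group of infants:

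- below 1500 g: 3 / (3 + 4) = 43%
- at or above 1500 g: 1 / (1 + 4) = 20%

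Next-morning rechecks after a scheduled visit (Days 9, 16, 23, 30) are not summarised either, because the scheduled value takes precedence. The scheduled exceedance that prompted the recheck is kept, so this loses information on duration, not on whether the infant exceeded 250 mg/dL.

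**2. What this could mean for infants, under assumed rates**

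Let r be the chance that a ramp-up sample exceeds 250 mg/dL, s the chance for a weekly sample, k the number of ramp-up samples and m = 4 weekly samples, all independent. These rates are assumptions.

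- All samples: P = 1 − (1 − r)^k (1 − s)^4
- Weekly samples only: P = 1 − (1 − s)^4
- Share missed = 1 − (weekly only / all)

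| r | s | k | Weekly only | All samples | Share missed |
|---|---|---|---|---|---|
| 2% | 2% | 1 | 7.8% | 9.6% | 19% |
| 2% | 2% | 3 | 7.8% | 13.2% | 41% |
| 5% | 2% | 1 | 7.8% | 12.4% | 37% |
| 5% | 2% | 3 | 7.8% | 20.9% | 63% |

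Even the weekly-only rate is not planned as an output. The comparison shows why an added count should use all samples and not just scheduled ones.

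**3. Whether the rate could be estimated usefully**

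SAP 8.8 gives 152 randomized patients at the interim. Assuming an even split, that is 152 / 2 = 76 per arm. Wilson 95% intervals for assumed counts are:

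- 4/76 (5%): 2.1% to 12.8%
- 8/76 (11%): 5.4% to 19.4%
- 15/76 (20%): 12.3% to 30.0%

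These are wide but informative for a descriptive safety table.

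**The case against.** The strongest reply is that the information appears elsewhere. Protocol 12.3.2.1 makes clinically significant out-of-range values adverse events. Table 3 in Protocol 13.2.1 calls an event clinically relevant if it led to an intervention, and withholding lipid may be read as one. SAP 8.12.4 reports treatment-emergent events by preferred term and arm without visit windows, so ramp-up events can appear there. SAP 8.6 and Table 14.3.5.4 summarise dose interruptions, and reasons for those over 4 hours are collected. The table shells are a separate document, so a layout by reason cannot be excluded.

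This stands in part, and it would be wrong to say that hypertriglyceridemia goes unreported. But the adverse-event route depends on each site's judgement, and the documents do not say that a TG hold counts as an intervention. The interruption summary states no breakdown by reason, and lipid may also be held for 4 hours before a draw from the infusion line. SAP 7.11 and 8.12.5 promise listings, but the SAP section 10 index as supplied shows no laboratory listing, and a listing gives no incidence by arm.

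A reader might also infer more than the documents support:

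- *The window rule causes the missing rate.* It does not. SAP 8.12.5 defines no such outcome, and removing 7.11 would not create one.
- *Omitted rechecks lower the incidence.* They do not when the triggering scheduled value is kept.
- *The protocol expects a smaller TG rise than with Intralipid.* Protocol 5.3 cites a phase 1 comparison with a different soybean emulsion; the benefit it expects over Intralipid is hepatic.
- *The comparison is biased toward no difference.* This is possible, but no rate or arm difference in the documents shows it.

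**Conclusion.** The gap is real and limited. No planned table gives the per-infant incidence of TG above 250 mg/dL by arm, and the by-visit summaries leave out the on-schedule ramp-up samples of infants starting parenteral nutrition in the study. The 43% and 20% are shares of required samples to Day 29 in that group. They are not shares of infants or of exceedances. Infants already on parenteral nutrition have fewer dose steps or none, and the documents do not give the size of either group. The 19% to 63% of affected infants missed rests on assumed per-sample rates and independence. The 76 per arm is also an assumption.

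All analyses are descriptive, so no test, error rate or primary result is affected. What changes is what the report can say about TG tolerance. This is a cheap improvement to safety reporting that is worth making.

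**What to change.** In SAP 8.12.5 add one descriptive table by treatment and NEC group, using all scheduled and unscheduled TG samples after the first dose:

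- number and percentage of infants with any TG above 250 mg/dL, overall and up to Day 7, with a risk difference and 95% confidence interval for the any-exceedance row;
- maximum TG per infant;
- number of TG samples per infant;
- number of infants with study drug held for TG, from the interruption reasons already collected.

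Add one sentence to SAP 7.11 stating that its value selection applies to by-visit tables only. Confirm that the laboratory listing promised in 8.12.5 is included in section 10.

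The cost is one table and one sentence, with no new data. The drawback is that infants sampled more often have more chances to exceed 250 mg/dL. The samples-per-infant row is there so that readers can judge this.

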8 STATISTICAL ANALYSIS

As only a small number of patients was enrolled after the interim analysis in stage 2 of the study, all data other than the primary endpoint will be presented for stages 1 and 2 combined and analyses will not be stratified by study stage.

8.1 Disposition

Patient disposition will be presented by underlying disease (No NEC / NEC) and treatment arm for all patients in stage 1 and stage 2 of the group-sequential design combined and for each stage separately. The composition of the analysis sets and those who completed or discontinued from the study will be presented by underlying disease and treatment arm and overall by absolute numbers and percentages. The reasons for early discontinuation will be listed and summarized descriptively.

8.2 Protocol Deviations

- Number and percentage of protocol deviations will be presented overall and by deviation type (major, minor), deviation review category (intent-to-treat, per protocol), and by the following deviation categories:
- inclusion/exclusion criteria
- informed consent issue
- out-of-window visit
- protocol required evaluation not completed
- physician decision
- parent / legal guardian decision
- investigational drug issue
- anthropometric measurement issue
- other

for each underlying disease group and treatment arm.

A listing of all events (sorted by criterion patient) will be included.

8.3 Demographic Data and Baseline Characteristics

Demographic and baseline characteristic data include postmenstrual and chronological ("post-natal") age, gender, race, ethnicity, body weight, length, head circumference (low for age, normal, high for age, section 8.11.1), and underlying disease at screening. In addition, liver laboratory values including bilirubin, triglycerides will be summarized by underlying disease and treatment at baseline.

Statistical Analysis Plan

FK Study Identifier: SMOF-018-CP3

8.4 Medical History

Medical history will be summarized by the following medical history categories as reported in the CRF for each treatment group:

- Allergy
- Head, ear, eyes, nose and throat (HEENT)
- Respiratory
- Cardiovascular
- Gastrointestinal
- Hepatic
- Genitourinary
- Immunologic
- Hematologic/Lymphatic
- Neurologic
- Endocrine/Metabolic
- Musculoskeletal
- Dermatologic
- Infectious Disease
- Other

A comprehensive data listing will also be included.

8.5 Prior and Concomitant Medication

Prior and concomitant medications are any medications, vitamins, dietary supplements and vaccinations received by the patient prior to and since signing Informed Consent.

Prior medications are medications started and ended before start of study medication, concomitant at baseline are medications started before or at baseline visit and ongoing during study treatment, and concomitant medications are medications given after baseline.

Prior and concomitant medications will be coded with the World Health Organization (WHO) drug dictionary and number and percentage of patients with the event will be summarized with descriptive statistics by level 2 (therapeutic / pharmacological subgroup) and level 4 (chemical / therapeutic / pharmacological subgroup) of the Anatomical Therapeutic Chemical Classification System (ATC) by treatment arm. A data listing will be included that shows all medications sorted by generic name and verbatim name. In addition, prior and concomitant medications will be listed for each patient.

Statistical Analysis Plan

FK Study Identifier: SMOF-018-CP3

